3.2.2 Immunotherapy Response Evaluation System

3.2.2.1 Primary Observation Indicators

(1) Time to Progression (TTP)

Definition: The time from the start of targeted - immunotherapy combination treatment to

the first time meeting the mRECIST progression criteria.

Evaluation Criteria:

Target lesions: The sum of the diameters of arterial - phase enhancement increases by $\geq 20\%$ compared to the baseline and the absolute value $\geq 5\text{mm}$;

Non - target lesions: New lesions appear or existing non - target lesions have definite progression;

Distant metastasis: New occurrences of lung, bone, or lymph node metastases.

(2) Objective Response Rate (ORR)

Definition: The proportion of patients achieving complete response (CR, disappearance of arterial - phase enhancement in all target lesions) and partial response (PR, the sum of the diameters of target lesions is reduced by $\geq 30\%$).

Evaluation Time: For each line of targeted - immunotherapy combination treatment regimen received by the patient, the determination is made simultaneously at Week 8, Week 16, Week 24 of the regimen treatment, and at disease progression (or regimen termination). If the patient changes the targeted - immunotherapy treatment regimen due to poor efficacy, the treatment cycle of the new regimen needs to be recorded separately (Weeks 8, 16, 24 are recalculated from the start time of the new regimen), and the CR/PR status is evaluated at the corresponding time points. In the final ORR calculation, the CR/PR status achieved by the patient in a certain regimen only corresponds to the treatment cycle and evaluation time of that regimen, that is, it is clearly associated with the efficacy data of the specific targeted - immunotherapy combination regimen (including the first regimen or the subsequent new regimens).

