3.2.2.2 Secondary Observation Indicators

(1) Core Indicators of Immunotherapy Response

① Progression - Free Survival (PFS)

Definition: The time from the start of targeted - immunotherapy combination treatment to the first disease progression (determined according to mRECIST) or death from any cause, whichever occurs first.

Evaluation Method: Combine imaging examinations (once every 8 weeks) and survival status follow - up, and use the Kaplan - Meier method to perform Log - rank test to compare the differences between groups.

② Overall Survival (OS)

Definition: The time from the start of targeted - immunotherapy combination treatment to the patient's death from any cause; for lost - to - follow - up patients, the last follow - up date is used as the censored data.

Evaluation Method: Record the survival status through regular telephone/outpatient follow - up, draw survival curves, and analyze the differences between groups.

Dynamic changes of tumor markers.

(2) Dynamic Monitoring Related to Tumors

Dynamic changes of tumor markers

Monitoring Indicators: Alpha - fetoprotein (AFP), protein induced by vitamin K absence or antagonist - II (PIVKA - II), detected once at baseline and every 4 weeks.

Judgment Criteria: An increase of $\geq 20\%$ compared to the baseline and lasting for more than 4 weeks, combined with imaging results to assist in predicting the progression

risk (such as the early warning value of marker increase before imaging progression).

(3) Evaluation of Treatment - Related Status

① Correlation with Liver Function Status

Evaluation Nodes: Collect liver function data (Child - Pugh class, total bilirubin, albumin, INR) simultaneously when disease progresses.

Analysis Logic: Compare with baseline liver function, exclude interfering factors such as drug - induced liver injury, and evaluate the direct impact of tumor progression on liver function injury.

② Survival Analysis after Progression

Record Content: Treatment adjustment plans after disease progression (changing targeted drugs, adding local treatments, etc.).

Analysis Indicators: Post - progression survival (PPS, the time from disease progression to death or the end of the study), and analyze the impact on survival by combining differences in treatment plans.

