3.2.3.2 Survival Analysis

Use the Kaplan - Meier method to draw survival curves of time to progression (TTP) and post - progression survival (PPS), and compare the survival differences between the new typing cohort and other typing cohorts through Log - rank test; use the Cox proportional hazards regression model to analyze the impact of 29 - gene set typing and clinical factors (such as Child - Pugh class, changes in tumor markers) on the progression risk.

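### Target-lesion progression for the primary endpoint TTP is measured from baseline instead of the smallest on-treatment sum, so responders must regrow far more than non-responders before they count as progressed

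*Protocol*

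**What the plan says.** Section 3.2.2.1 (1) of the protocol defines TTP as running from the start of combination treatment to "the first time meeting the mRECIST progression criteria". It then writes the criteria out. For target lesions, the sum of arterial-phase enhancing diameters must rise by at least 20% "compared to the baseline and the absolute value" must be at least 5 mm. Two other routes also count: "New lesions appear or existing non - target lesions have definite progression", and new distant metastases.

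In the same section, partial response is given as "PR, the sum of the diameters of target lesions is reduced by" at least 30%, with no reference sum named. Complete response is loss of arterial enhancement in all target lesions.

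Section 3.2.2.2 defines PFS by "first disease progression (determined according to mRECIST) or death from any cause" without writing out a threshold. Post-progression survival (PPS) is "the time from disease progression to death or the end of the study", with no criterion for the progression date.

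Section 3.2.3.2 will "compare the survival differences between the new typing cohort and other typing cohorts through Log - rank test" for TTP and PPS, and will model progression risk by Cox regression. Section II expects a higher response rate in the new subtype. Section IV plans 100 patients in the new-subtype cohort and 250 in the others.

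**The concern.** With a baseline reference, the growth needed to reach progression depends on how far the tumour first shrank. A patient who never shrank is close to the threshold. A responder must first regain everything that was lost and then grow a further 20%. In the extreme case, target lesions in complete response could re-enhance to their full original size and the target-lesion criterion would still not be met.

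If the new subtype does respond more often, its target-lesion events come later by definition, even when regrowth begins at the same time in both cohorts. The two primary indicators, TTP and ORR, would then partly measure the same thing, and the distortion favours the study's hypothesis. A larger sample would not remove it.

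There is also a consistency problem. TTP has a written baseline rule, PFS cites mRECIST alone, and PPS cites nothing. Ten hospitals could therefore date progression differently, or date it differently for TTP and PFS in the same patient.

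**Working it through.** **Inputs from the protocol (3.2.2.1).** Progression at +20% over baseline and 5 mm; partial response at -30%. Two readings are assumed: the 5 mm is an absolute increase, and the response reduction is taken from baseline in the enhancing sum. The protocol gives no figure of its own to reproduce on this point.

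**Formulas.** Let S0 be the baseline sum, d the fractional shrinkage and N = S0 × (1 - d) the low point.

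- Threshold as written: max(1.2 × S0, S0 + 5 mm).
- Threshold with a low-point reference: max(1.2 × N, N + 5 mm).
- Regrowth needed: threshold / N - 1.

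The 20% condition governs the written rule once 0.2 × S0 ≥ 5 mm, that is S0 ≥ 5 / 0.20 = 25 mm. From there the regrowth needed is 1.2 / (1 - d) - 1:

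- no shrinkage: 1.2 / 1.0 - 1 = 20%
- -30%: 1.2 / 0.7 - 1 = 71%
- -50%: 1.2 / 0.5 - 1 = 140%
- -70%: 1.2 / 0.3 - 1 = 300%

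**Worked cases.**

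| Baseline sum | Low point | Regrowth needed as written | Regrowth needed from low point |
|---|---|---|---|
| 50 mm | 35 mm (-30%) | 25 mm (71%) | 7 mm (20%) |
| 50 mm | 25 mm (-50%) | 35 mm (140%) | 5 mm (20%) |
| 50 mm | 15 mm (-70%) | 45 mm (300%) | 5 mm (33%) |
| 20 mm | 6 mm (-70%) | 19 mm (317%) | 5 mm (83%) |

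Below 25 mm the 5 mm condition raises the figures under the written rule. At S0 = 20 mm the threshold is 25 mm: 25 / 20 - 1 = 25% without shrinkage and 25 / 14 - 1 = 79% at -30%.

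**Effect on the group comparison (illustrative simulation).** The protocol gives no response rates, shrinkage depths or growth rates, so these are assumptions:

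- Responders shrink by 30% to 80% and non-responders by 0% to 29%, both uniform.
- Time to start of regrowth is exponential with median 4 months in both groups.
- The sum doubles in 2 or 4 months.
- Baseline sums are uniform on 30 to 100 mm or 15 to 60 mm.
- Censoring is uniform over 12 to 30 months.
- Other progression routes occur at an equal rate in both groups, set so that target lesions cause 100% or 50% of events.

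The scan interval of 8 weeks is the protocol's (3.2.2.2, PFS evaluation). Hazard ratios come from a Cox model, averaged over 6 replicates of 40,000 vs 100,000 patients (replicate SD 0.004 to 0.007).

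Hazard ratio, new subtype vs others, rule as written, sums 30 to 100 mm:

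| ORR | Events from target lesions | Doubling 2 months | Doubling 4 months |
|---|---|---|---|
| 40% vs 30% | 100% | 0.969 | 0.939 |
| 40% vs 30% | 50% | 0.979 | 0.963 |
| 50% vs 25% | 100% | 0.921 | 0.853 |
| 50% vs 25% | 50% | 0.942 | 0.904 |

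Sums of 15 to 60 mm give the same values to within 0.001. With a low-point reference the hazard ratio is 0.992 to 1.002 for the larger sums. For the smaller sums, where the 5 mm floor still acts, it is 0.991 to 0.999 (40% vs 30%) and 0.973 to 0.991 (50% vs 25%). With equal response rates (30% vs 30%) both rules give about 1.00.

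**Against the study's precision.** With 100 and 250 patients and simulated event shares of 0.90 to 0.99, SE(log HR) = sqrt(1/E1 + 1/E0) = 0.119 to 0.124, where E1 and E0 are the event counts. The shift is -ln(HR) / SE:

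- 40% vs 30%: 0.18 to 0.51 SE; a two-sided 5% test rejects 5% to 8% of the time.
- 50% vs 25%: 0.50 to 1.28 SE; rejection 8% to 25%. At the top, -ln(0.853) / 0.124 = 1.28.

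**The case against.** The strongest reply is that mRECIST governs. TTP is defined by that standard, PFS and the efficacy judgment in 3.2.3.3 also follow it, and the target-lesion line may be only a summary. The protocol does not say which reference sum the standard uses, so how often the baseline wording would be applied is not known. That uncertainty stands. It does not clear the text, because baseline is the only reference the protocol writes out for those who will date progression.

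Second, time until the sum exceeds baseline by 20% is a coherent quantity, and a tumour that shrank does reach it later. This stands in part. The 8% to 25% is not an ordinary false-positive rate. It is how often TTP would appear to differ when regrowth starts at the same time in both groups but response rates differ. The overlap with ORR remains.

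Third, the effect is modest and diluted by the other progression routes. That is true at 40% vs 30%. The 25% figure needs a doubled response rate, every event from target lesions, and the slower growth, all at once.

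Fourth, the event shares of 0.90 to 0.99 ignore dropout. With 60% events and the hazard ratio held at 0.853, SE = sqrt(1/60 + 1/150) = 0.153, the shift is 1.04 and rejection is about 18%. But the hazard ratio does not stay put: adding dropout that cuts events to about 61% to 62% moves it further from 1, and worst-case rejection stays near 23%.

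**Conclusion.** The concern holds: the criterion is wrong as written and should be corrected. The regrowth figures (71%, 140% and 300% against 20%, for baseline sums of 25 mm or more) follow directly from the protocol's own thresholds, given the two readings stated above. The direction is also clear: if the new subtype responds more often, its target-lesion TTP events are delayed by the definition. With equal response rates there is no bias.

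The size is not known. Under the assumed scenarios it is 0.2 to 0.5 SE of the log hazard ratio at ORR 40% vs 30%, and 0.5 to 1.3 SE at 50% vs 25%. Those values depend on assumed response rates, shrinkage depth, growth rate, baseline sums and event mix, and on assessors using the baseline wording as it stands.

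**What to change.** In section 3.2.2.1 (1), change the reference for the 20% rise from baseline to the smallest sum recorded since treatment start, baseline included. Keep the 5 mm condition and word it as an absolute increase over that same sum. Add one sentence stating that this single progression definition applies to TTP, PFS and the start date of PPS. This is best settled before progression dates are abstracted.

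The cost is protocol wording plus some data work. Measured enhancing sums are needed at each available scan. Response and the present progression rule already call for them, so the main addition is tracking the running minimum. For prospective patients the PFS method says "Combine imaging examinations (once every 8 weeks) and survival status follow - up", with no stated end; the Week 8, 16 and 24 schedule concerns ORR only. Retrospective cases depend on routine CT/MRI reports, where sums may have to be measured again. Some progression dates will move earlier and median TTP will be shorter.

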3.2.2.2 Secondary Observation Indicators

(1) Core Indicators of Immunotherapy Response

① Progression - Free Survival (PFS)

Definition: The time from the start of targeted - immunotherapy combination treatment to the first disease progression (determined according to mRECIST) or death from any cause, whichever occurs first.

Evaluation Method: Combine imaging examinations (once every 8 weeks) and survival status follow - up, and use the Kaplan - Meier method to perform Log - rank test to compare the differences between groups.

② Overall Survival (OS)

Definition: The time from the start of targeted - immunotherapy combination treatment to the patient's death from any cause; for lost - to - follow - up patients, the last follow - up date is used as the censored data.

Evaluation Method: Record the survival status through regular telephone/outpatient follow - up, draw survival curves, and analyze the differences between groups.

Dynamic changes of tumor markers.

(2) Dynamic Monitoring Related to Tumors

Dynamic changes of tumor markers

Monitoring Indicators: Alpha - fetoprotein (AFP), protein induced by vitamin K absence or antagonist - II (PIVKA - II), detected once at baseline and every 4 weeks.

Judgment Criteria: An increase of $\geq 20\%$ compared to the baseline and lasting for more than 4 weeks, combined with imaging results to assist in predicting the progression

risk (such as the early warning value of marker increase before imaging progression).

(3) Evaluation of Treatment - Related Status

① Correlation with Liver Function Status

Evaluation Nodes: Collect liver function data (Child - Pugh class, total bilirubin, albumin, INR) simultaneously when disease progresses.

Analysis Logic: Compare with baseline liver function, exclude interfering factors such as drug - induced liver injury, and evaluate the direct impact of tumor progression on liver function injury.

② Survival Analysis after Progression

Record Content: Treatment adjustment plans after disease progression (changing targeted drugs, adding local treatments, etc.).

Analysis Indicators: Post - progression survival (PPS, the time from disease progression to death or the end of the study), and analyze the impact on survival by combining differences in treatment plans.

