3.2.1.2 Clinical Data Integration

Structured extraction of subjects' baseline data (age, gender, Child - Pugh class, etc.), treatment information (targeted - immunotherapy combination regimen, dosage, and cycle, etc.), imaging evaluation (enhanced CT/MRI reports, etc.), and survival status (last follow - up date or death time, etc.) from the electronic medical record system. Simultaneously collect AFP (electrochemiluminescence method), PIVKA - II (enzyme - linked immunosorbent assay), and liver function biochemical data (total bilirubin, albumin, INR, etc.). The detection frequency matches the imaging evaluation cycle (that is, equivalent to clinical routine).

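### Comparing liver function at progression with baseline, in progressors only, cannot separate the effect of progression from change over elapsed time

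*Protocol*

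**What the plan says.** Protocol section 3.2.2.2 (3), item 1 (correlation with liver function status), fixes three things.

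- **When:** "Collect liver function data (Child - Pugh class, total bilirubin, albumin, INR) simultaneously when disease progresses".
- **Against what, and for what conclusion:** "Compare with baseline liver function, exclude interfering factors such as drug - induced liver injury, and evaluate the direct impact of tumor progression on liver function".
- **Confounding:** the same sentence asks that interfering factors be set aside, with drug-induced liver injury as the example.

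The item names no patients without progression as comparator and no on-treatment value before progression.

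Section 3.2.1.2 separately collects "liver function biochemical data (total bilirubin, albumin, INR, etc".), and says of these laboratory data: "The detection frequency matches the imaging evaluation cycle (that is, equivalent to clinical routine"). Section 3.2.2.2 (1) puts imaging at 8 weeks: "Combine imaging examinations (once every 8 weeks) and survival status follow - up". Child-Pugh class appears in section 3.2.1.2 among the baseline items, "Structured extraction of subjects' baseline data (age, gender, Child - Pugh class, etc".), and again at progression. It is not named among the serial items.

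Section 3.2.3.1 lists liver function indicators under tests for independent groups (t-test, analysis of variance, Mann-Whitney, Kruskal-Wallis). It names no paired or longitudinal method.

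**The concern.** The change from baseline to progression contains everything that happened in between: the course of the underlying liver disease, drug effects nobody recognised, and recovery from local treatment, which inclusion criterion 3 allows up to 4 weeks before the combination starts. These need not act in the same direction. Recovery from earlier local treatment would mask damage, while worsening liver disease would mimic it.

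Elapsed time also varies by design. A patient who progresses early has a short interval and a late progressor a long one, so under any steady drift the apparent damage grows with time to progression even if progression does nothing. With no same-time values from patients who have not progressed, the analysis cannot show whether a drift exists.

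At stake is a causal statement about tumour progression and liver injury that the stated contrast cannot support.

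**Working it through.** The protocol gives no expected change, standard deviation or power for this analysis, so there is no figure of its own to reproduce. What follows shows the mechanism and how its size depends on an assumed drift.

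**1. Arithmetic.** Let liver function drift by x per 8-week cycle, regardless of progression, with a true progression effect of 0. Then

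apparent effect = x × (week of progression ÷ 8)

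- Week 8: 8 ÷ 8 = 1, so 1x.
- Week 48: 48 ÷ 8 = 6, so 6x.

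Subtracting the change over the same weeks in progression-free patients who share the drift gives 1x - 1x = 0 and 6x - 6x = 0.

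**2. Inputs for an illustration.**

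- From the protocol: 350 patients (section IV), 8-weekly visits (section 3.2.2.2), p < 0.05 (section 3.2.3.4).
- Assumed, not in the protocol: follow-up to week 48; exponential time to progression with median 24 or 40 weeks; albumin with baseline mean 38 g/L and SD 4; within-patient visit SD 3 g/L; linear drift of 0 to -1.0 g/L per 8 weeks.

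**3. Average number of cycles to progression among progressors.** Let q be the chance of passing one 8-week cycle without progression. Then mean cycles = 1/(1 - q) - 6q⁶/(1 - q⁶).

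- Median 24 weeks: q = 2^(-8/24) = 0.794 and q⁶ = 0.250. Mean = 4.85 - 2.00 = 2.85 cycles, with 350 × 0.750 ≈ 262 progressors.
- Median 40 weeks: q = 2^(-8/40) = 0.871 and q⁶ = 0.435. Mean = 7.72 - 4.62 = 3.10 cycles, with 350 × 0.565 ≈ 198 progressors.

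The expected bias is the drift times these means.

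**4. Simulation, true progression effect 0** (5,000 runs per row):

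| Drift per 8 weeks (g/L) | Median TTP (weeks) | Progression minus baseline (g/L) | Runs with p < 0.05 | Same-visit contrast with progression-free patients (g/L) |
|---|---|---|---|---|
| 0 | 24 | 0.00 | 5% | 0.00 |
| 0 | 40 | 0.00 | 5% | 0.00 |
| -0.25 | 24 | -0.71 | 78% | 0.00 |
| -0.25 | 40 | -0.78 | 72% | 0.00 |
| -0.5 | 24 | -1.43 | over 99% | about 0 |
| -0.5 | 40 | -1.55 | over 99% | 0.00 |
| -1.0 | 24 | -2.85 | 100% | 0.00 |
| -1.0 | 40 | -3.10 | 100% | 0.00 |

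The third column agrees with step 3; for example, -1.0 × 2.85 = -2.85.

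**5. With a true effect of -1.0 g/L** (400 runs per setting), the same-visit contrast gave about -1.0 throughout. The baseline contrast ran from -1.0 with no drift to -4.1 at a drift of -1.0 g/L.

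**6. Limit of the same-visit contrast.** It returns the truth only if both groups drift alike. If future progressors drift by -0.5 and progression-free patients by -0.25 g/L per cycle, the residual bias at median 24 weeks is 2.85 × (-0.5 + 0.25) = -0.71 g/L. That is half of the -1.43 g/L under the baseline contrast, but not zero.

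**The case against.** The best defence is that the protocol gives only a short line of analysis logic, and that comparator, time adjustment and the rule for drug injury are ordinary SAP content. That stands for the drug-injury rule and the choice of test. It does not stand for the contrast: the time point, the comparator and the conclusion are all written down, and a test applied to that contrast does not remove the problem.

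Several stronger readings are tempting but unsupported:

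- *Drug effects are counted as progression effects.* The text says drug-induced liver injury is to be excluded. Only unrecognised injury can remain. Nor does the text say that patients are dropped, or when the judgement is made.
- *Liver function is measured only at progression.* That is true of this analysis, not of data collection, since section 3.2.1.2 has serial biochemistry.
- *Everything needed is already in hand.* Serial Child-Pugh class is not listed. The frequency is tied to clinical routine and part of the study is retrospective (section VI), so complete same-week values are not assured.
- *A study objective fails.* Section II concerns differences in response between subtypes. Liver function is a supporting indicator, and its own heading speaks of correlation.
- *Late progressors will look worse.* This follows only if there is a worsening drift, and the protocol gives none.

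It is also fair to say that matching by week is no complete cure, because patients still progression-free are a selected group (step 6).

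**Conclusion.** The point holds in a limited form. Followed as written, section 3.2.2.2 (3) item 1 credits any change over elapsed time to progression, so its causal wording is not supported. Excluding recognised drug injury does not alter this.

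Size and direction rest wholly on a drift the protocol does not state. The bias is zero with no drift. Under the assumed albumin drifts of -0.25 to -1.0 g/L per 8 weeks it is about -0.7 to -3.1 g/L with no true effect, and it would reverse in sign if values recover over time. These figures assume linear drift unrelated to progression and are illustrations, not predictions.

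The consequence is confined to one secondary observation indicator. TTP, ORR, PFS, OS and the subtype comparison do not depend on it. The change is worth making because it is cheap and prevents an unsupported causal conclusion.

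**What to change.** Amend section 3.2.2.2 (3), item 1:

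1. For bilirubin, albumin and INR, use the values collected on the imaging cycle in all patients. Compare the change up to progression with the change over the same weeks in patients still progression-free, adjusted for baseline liver function. A longitudinal model with time and time-varying progression status is an equivalent route.
2. Keep Child-Pugh class as a descriptive comparison of baseline with progression, since it is not listed serially.
3. Replace *direct impact* with *association*.
4. State how suspected drug-induced liver injury is identified and handled, here or in the SAP.

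The cost is protocol wording and some extra analysis, with no new tests. Two weaknesses remain and should be reported: routine-care values may be incomplete, notably in the retrospective part, and progression-free patients may differ from progressors, so selection is reduced but not removed. If the sponsor prefers not to add the comparison, the minimum is to describe the item as change in liver function between baseline and progression, with no causal claim.

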3.1.3 Withdrawal Criteria

- ① The subject voluntarily requests to withdraw from the study and signs a written withdrawal statement.
- ② Severe adverse events occur during the study (such as grade 3 or above immune - related adverse reactions, severe infections, etc.), and after the researcher's evaluation, it is considered that continued participation in the study may endanger the subject's safety.
- ③ The subject does not comply with the research protocol, including but not limited to: failure to follow up at the specified time, refusal to complete necessary examinations, unauthorized acceptance of other antineoplastic treatments, etc.
- ④ It is found during the study that the subject does not meet the inclusion criteria of this study (such as the previous treatment history does not meet the requirements found in the baseline data verification).
- ⑤ The subject is unable to continue participating in the study due to disease progression, death, and other reasons.
- ⑥ The study is terminated in advance (such as protocol revision, ethical committee requiring termination, etc.).

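### Comparing post-progression survival by treatment started after progression is open to immortal-time bias, and the subtype log-rank test of PPS rests on progressors only

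*Protocol*

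**What the plan says.** Protocol 3.2.2.2, under survival analysis after progression, measures PPS as "the time from disease progression to death or the end of the study". It records changes of treatment made after progression, such as a new targeted drug or added local treatment, and intends to "analyze the impact on survival by combining differences in treatment plans". It names no model, exposure definition or landmark for this.

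Protocol 3.2.3.2 assigns TTP and PPS to Kaplan-Meier curves and will "compare the survival differences between the new typing cohort and other typing cohorts through Log - rank test". Section 3.2.3.4 sets P < 0.05 as the criterion for significance. The only Cox model described in 3.2.3.2 concerns the risk of progression, so it does not cover survival after progression.

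Two other places bear on the point. The OS definition in 3.2.2.2 carries a censoring sentence ("for lost - to - follow - up patients, the last follow - up date is used as the censored data"), while the PPS definition carries none. Section 3.1.3, item 5, lists as a ground for withdrawal: "The subject is unable to continue participating in the study due to disease progression, death, and other reasons".

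**The concern.** There are two separate problems.

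**Treatment after progression.** The PPS clock starts at progression, and the treatment of interest starts later. A patient who dies before the new treatment begins falls into the untreated group. A patient in the treated group could not, by definition, have died during the wait. Grouping patients by what they received and counting time from progression credits that wait to the treatment, so even an ineffective treatment appears to prolong survival. The result could be read as guidance on what to do after progression.

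**Subtype comparison.** PPS exists only for patients who have progressed. Section II expects the new subtype to respond better, and TTP is a primary indicator. If that expectation is right, the subtypes contribute differently selected sets of patients to the PPS analysis. A log-rank difference there mixes any effect on survival with that selection.

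**Working it through.** The protocol states no PPS median, event count, hazard ratio or follow-up length, so there is no figure to reproduce. All inputs below are assumptions and are varied.

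**1. Closed-form check with unlimited follow-up and no treatment effect.**

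- PPS is exponential with median 8 months: λ = ln 2 / 8 = 0.0866 per month, so 1/λ = 11.54 months.
- 60% are intended for new treatment. The delay is exponential with mean d months: μ = 1/d.
- Treated (intended, and alive at start): mean PPS = 1/λ + 1/(λ+μ).
- Untreated: 0.4 of all patients were never intended (mean 1/λ), and 0.6·λ/(λ+μ) died before starting (mean 1/(λ+μ)).
- Apparent hazard ratio = deaths per person-month in treated ÷ deaths per person-month in untreated.

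For d = 1:

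- λ+μ = 1.0866 and 1/(λ+μ) = 0.920.
- Treated rate = 1/(11.54 + 0.92) = 0.0802.
- Untreated deaths = 0.4 + 0.6 × 0.0797 = 0.4478. Untreated time = 0.4 × 11.54 + 0.0478 × 0.920 = 4.661. Rate = 0.0961.
- Ratio = 0.0802/0.0961 = 0.84 (0.835 before rounding the rates).

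For d = 3:

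- λ+μ = 0.4200 and 1/(λ+μ) = 2.381.
- Treated rate = 1/(11.54 + 2.38) = 0.0718.
- Untreated deaths = 0.4 + 0.6 × 0.2063 = 0.5238. Untreated time = 4.617 + 0.1238 × 2.381 = 4.911. Rate = 0.1067.
- Ratio = 0.67.

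**2. Limited follow-up, by simulation.** The inputs are the same, but follow-up after progression is uniform over the stated range. A patient counts as treated if treatment starts before death or the end of follow-up.

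| Mean delay | Follow-up 2–20 months | Follow-up 12–36 months |
|---|---|---|
| 0.25 months | 0.92 | 0.94 |
| 1 month | 0.74 | 0.81 |
| 3 months | 0.56 | 0.63 |

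The true value in every cell is 1.00. When the months before treatment starts are counted as untreated time (time-dependent exposure), the estimate returns to about 1.00.

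**3. Sensitivity to the assumed median.** With follow-up fixed at 24 months and median PPS of 8, 12 and 18 months, the false hazard ratio is 0.81, 0.85 and 0.87 at a 1-month mean delay, and 0.63, 0.67 and 0.68 at 3 months. The direction does not change. The size depends mainly on the delay and the length of follow-up.

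**4. Subtype log-rank.** No arithmetic is possible here, because the protocol gives no progression rates. The logic is as follows. Section IV expects 100 and 250 patients, but PPS uses only those who progress. Under the study's own hypothesis, that fraction, and the kind of patient in it, differs by subtype. Even if the full cohorts were comparable, the progressors need not be. The direction of the resulting error cannot be determined from the protocol. OS starts at the same point for everyone and does not add this selection, although it remains an observational comparison.

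**The case against.** The strongest reply is that the protocol fixes no treatment analysis. It states an aim. Treatment could be classified by the plan made at progression, used only for description, or handled by landmark in an analysis plan that is not shown. That stands: the bias is a risk left open, not a stated design choice. With delays of about a week it is also small (0.92–0.94). A reader might infer that the log-rank test compares treatments, but 3.2.3.2 applies it to typing cohorts only.

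It is also fair to say that PPS can only ever be measured in progressors and is a secondary indicator that Section II does not name. A conditional comparison is legitimate if read as one. What remains is that 3.2.3.2 makes it a formal between-subtype test.

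A stronger reading is tempting: that study end counts as a PPS event. The documents do not say so. Kaplan-Meier and log-rank ordinarily censor patients who are alive, and 3.2.1.2 collects the last follow-up or death date needed to do it. The contrast with OS is weak, since its censoring sentence covers only loss to follow-up, and TTP and PFS have no such sentence either. Even on the literal reading, the distortion depends on follow-up. With 2–20 months, 43% are alive at study end and the median falls from 8.0 to 5.5 months. With 12–36 months, 15% are alive and the median is 7.98. With equal follow-up between groups, that coding would dilute a subtype difference while type I error stays near 5%.

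A reader might also infer that withdrawal item 5 removes every progressor. It covers those unable to continue, and 3.2.2.2 plainly expects data after progression.

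**Conclusion.** The point holds in two parts. First, survival is to be related to treatment begun after the PPS time zero, with no stated protection against immortal time. Second, PPS is formally tested between subtypes in a subset that depends on the outcome the subtype is expected to change.

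The treatment bias is negligible to large depending on delay: a false hazard ratio from 0.94 down to 0.56 over mean delays of 0.25 to 3 months. This rests on assumed exponential survival with median 8 months, 60% intended for new treatment, and classification by treatment received. The selection problem cannot be sized from the protocol.

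The phrase about study end and withdrawal item 5 are matters of wording. Neither shows that study end is coded as an event or that all progressors leave follow-up. Since PPS is secondary, the severity is minor to moderate.

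**What to change.** - In 3.2.2.2, state that post-progression treatment is analysed as a time-dependent covariate, or from a fixed landmark after progression with treatment classified at that landmark.
- In 3.2.3.2, report PPS by subtype descriptively (curves, medians, intervals) without a significance claim, and use OS, whose group comparison 3.2.2.2 already plans, as the subtype survival comparison.
- As a clarification, define the PPS event as death from any cause only, with patients alive censored at the last date known alive.
- Reconcile 3.1.3 item 5 with the survival follow-up after progression that PPS and OS need.

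The cost is a few sentences and a few lines of survival code. Death and last follow-up dates are already collected. The start date of each post-progression treatment must be recorded along with the change itself. The one real loss is a formal test.
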